3.2 Interim analyses

No interim analyses planned.

3.3 Subgroup analyses

The following subgroups will be additionally considered in the analysis of the primary endpoint:

- Type of indication (Stone treatment / Stricture treatment)
- Type of reconstructive surgery (Billroth II gastrectomy / Whipple's duodenopancreatectomy Roux-en-Y / Gastric bypass / Hepaticojejunostomy)
- Presence/absence of biliodigestive anastomosis (reimplanted papilla)
- First 10 cases per investigator versus subsequent cases (to account for learning curve)

3.4 Derived Data and Data Sets

3.4.1 Rules for incomplete data

Missing data will not be replaced.

3.4.2 Rules for efficacy

None.

3.4.3 Rules for adverse events

Seriousness: 0 ≈ 'no', 1 ≈ 'yes'.

Attribution of the AE to the PowerSpiral Device

A frequency table will be presented showing the information on attribution of the AE to the PowerSpiral device using the categorization given on the CRFs:

1 ≈ 'not related', 2 ≈ 'unlikely', 3 ≈ 'possible', 4 ≈ 'probable', 5 ≈ 'causal relationship'.

Moreover, this categorization will be used in data listings.

3.4.4 Rules for laboratory data

Not applicable.

3.4.5 Rules for vital signs

Not applicable.

3.4.6 Rules for physical examination

Not applicable.

3.4.7 Other rules

None.

3.5 Demography, Medical History, Concomitant Medication, Study Procedures

Descriptive statistics (n, mean, standard deviation, median, 25th and 75th percentiles, minimum and maximum) will be calculated for quantitative variables; frequency counts by category will be given for qualitative variables. Confidence intervals will be given where appropriate. If not stated otherwise, these intervals will be two sided in each case and provide 95% confidence. Individual listings will be provided for each parameter examined in this study.

Concomitant medication and medical history will be listed only (if no codes are available).

3.6 Efficacy Analysis

The following efficacy analyses will be performed based on the ITT population:

- The total success rate (the number of therapeutic successes divided by the number of patients who received an enteroscopy) will be computed alongside with its 95% Clopper-Pearson confidence interval.
- The enteroscopy success rate (percentage of procedures with the ability to reach the major papilla or the biliary anastomosis) will be presented alongside its 95% Clopper-Pearson confidence interval.
- The biliary cannulation success rate (percentage of procedures with the ability to selectively cannulate the bile duct and conduct a cholangiography in relation to all cases with enteroscopy success) will be presented alongside its 95% Clopper-Pearson confidence interval.
- The therapeutic (procedural) success rate (percentage of procedures in which the intended treatment could be successfully completed after successful cannulation) will be presented alongside its 95% Clopper-Pearson confidence interval.
- The total procedure time (period in minutes needed to complete the procedure) will be summarized descriptively.
- The enteroscopy time will be summarized descriptively.
- The outcomes for the items in the user feedback for the judgement of handling characteristics and other aspects will be tabulated in frequency tables.

3.7 Safety Analysis

3.7.1 Adverse Events

The frequencies of adverse events, serious adverse events and device deficiencies will be reported in summary tables. These tables will show the number of subjects per group presenting a (serious) adverse event and the incidence of its occurrence.

Tabulations will be provided for system organ class and stratified by relation to the investigational product. Any withdrawals from the study due to adverse events will be reported. All measures taken due to adverse events will be reported.

AEs of special interest

- Number of patients with pancreatitis (including hyperamylasemia)
- Number of patients with bleeding
- Number of patients with mucosal damage

For pre-treatment events summary tables and listings will be provided.

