Endpoints	
Parameter for analysis:
 
 • Total success rate: Defined as the combined percentage of Enteroscopy success rate, Biliary Cannulation success rate and Procedural (Therapeutic) success rate. • Enteroscopy success rate: Defined as the percentage of procedures with the ability to reach the major papilla or the biliary anastomosis. • Biliary Cannulation success rate: Defined as the percentage of procedures with the ability to selectively cannulate the bile duct and conduct a cholangiography. • Therapeutic (Procedural) success rate: Defined as the percentage of procedures in which the intended treatment could be successfully completed. • Total procedure time: (starting with oral insertion until final withdrawal of the device). • Enteroscopy time: (starting with oral insertion until reaching the papilla or the biliary anastomosis). • Safety: Incidence (% of subjects) and frequency (no. of subjects) with Serious Adverse Events (SAEs) and Device Deficiencies (DD) which meet the severity grading of moderate or severe for the following categories: 
 ▪ Enteroscopy-associated complications (mainly bleeding and perforation(s)) ▪ ERCP-related complications (Dumonceau et al. 2020) ▪ Sedation / anesthesia related complications ▪ other • User feedback and assessment of handling characteristics of the device.
Study Design	International, multicenter, open label, non-randomized, prospective, observational study.
Sample Size	The study consists of two phases: Phase A which comprises deep enteroscopies only [completed by the time Phase B will start] and Phase B,

Clinical Investigation Plan

CIP Reference No.:2018-GI (OEKG) -01. The SAMISEN study - Final Version 03 - Date 28-Jun-2021

	
which includes ERCP in patients with surgically altered GI anatomy only.
 
For Phase B: Approximately 4-5 sites experienced both in conventional ERCP as well as in ERCP in patients presenting with previous GI surgery will proceed to Phase B of this study.
 
100 (ERCP) patients will be enrolled in this exploratory study.

Timelines	
Study Start (Enrollment of First Patient) is planned for Phase B in November 2021.
 
Enrollment period: approximately 12-18 months.
 
Study closure of Phase B is expected before end of 2022.
 
Please note: Phase B will start after completion of Phase A. The results from the Phase A will be reported independently from Phase B.

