3.1.3 Variables in the Clinical Investigation

It is a prospective and observational Registry without any additional procedure beyond clinical practice. The small-bowel enteroscopy for Phase A and ERCP for Phase B has to be performed according the medical standard. Serious Adverse Events (SAE) and Device Deficiencies (DD) must be documented.

For phase B the following parameters will be analyzed:

- **Total success rate:** Defined as the combined percentage of Enteroscopy success rate, Biliary Cannulation success rate and Procedural (Therapeutic) success rate.
- **Enteroscopy success rate:** Defined as the percentage of procedures with the ability to reach the major papilla or the biliary anastomosis.
- **Biliary Cannulation success rate:** Defined as the percentage of procedures with the ability to selectively cannulate the bile duct and conduct a cholangiography.
- **Therapeutic (Procedural) success rate:** Defined as the percentage of procedures in which the intended treatment could be successfully completed.
- **Total procedure time:** (starting with oral insertion until final withdrawal of the device).
- **Enteroscopy time:** (starting with oral insertion until reaching the papilla or the biliary anastomosis).
- **Safety:** Incidence (% of subjects) and frequency (no. of subjects) with Serious Adverse Events (SAEs) and Device Deficiencies (DD) which meet the severity grading of moderate or severe for the following categories:
 - Enteroscopy-associated complications (mainly bleeding and perforation(s))

Clinical Investigation Plan

CIP Reference No.:2018-GI (OEKG) -01. The **SAMISEN** study - Final Version 03 - Date 28-Jun-2021

- ERCP-related complications (Dumonceau et al. 2020):
- Sedation / anesthesia related complications
- other

User feedback and assessment of handling characteristics of the device.

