4.1.3 Safety evaluation

The following safety variables will be collected:

- Enteroscopy-associated Serious adverse events during and after enteroscopy procedure
- ERCP-related Serious adverse events (Dumonceau et al. 2020)
- Sedation / anesthesia related Serious adverse events
- Other Serious adverse events (procedure or product related)
- Adverse events during enteroscopy and ERCP procedure
- Adverse event of interest are: bleeding, mucosal damage and pancreatitis (including hyperamylasemia)

The safety variables will be tabulated for all study participants.

Adverse events data will be processed in the statistical analysis after coding with the most recent version of MedDRA.

AEs and device deficiencies will be presented in summary tables. These tables will show the number of subjects per group presenting an adverse event and the incidence of its occurrence. Adverse events will be grouped by system organ class and stratified by severity (mild, moderate, severe) and by relation to study treatment (unrelated or related according to the categories definite, probable and possible).

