11.2 Documentation

11.2.1 (Serious) Adverse Events / Adverse Device Effects

Independent from a possible relation to the investigational device, every AE spontaneously reported by the subject or observed by the investigator will be reported on the appropriate page of the case report form. Furthermore, the investigator shall actively ask the subject about the occurrence of any (S)AE at each visit and note any abnormal laboratory findings. For each adverse event the following information shall be documented:

- Description of the event (diagnosis and symptoms in verbatim terms). For the most common ERCP-related adverse events the following terms could be selected:
 - Pancreatitis
 - Cholangitis
 - Cholecystitis
 - Bleeding
 - Perforation (according (Stapfer 2000)
 - Type I Duodenal wall perforation (by the endoscope)
 - Type II Periampullary perforation (by sphincterotomy/ precut)
 - Type III Biliary or pancreatic duct perforation (by intraductal instrumentation)
 - Type IV Retroperitoneal gas alone
 - Sedation-related AEs
- Outcome,
- Seriousness,
- Duration (start date and stop date),
- Causal relationship to the investigational device.
Causality assessment will be done by the investigator using a 5-category system (no related / unlikely / possible / probable / causal relationship).
- Any therapy or corrective action initiated including.

The results of any complementary tests performed (laboratory tests, ECG, etc.) must be pseudonymized by the investigator prior to forwarding information to the sponsor. A period of 4 weeks for follow up of AEs after the subject has routinely completed or prematurely terminated the study seems sufficient. This means that any additional information needed to assess the (S)AE should be collected and documented in the respective CRF within one month after occurrence.

Clinical Investigation Plan

CIP Reference No.:2018-GI (OEKG) -01. The **SAMISEN** study - Final Version 03 - Date 28-Jun-2021

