2.5 Safety Variables

The following safety variables will be collected:

- Enteroscopy-associated serious adverse events during and after enteroscopy procedure
- ERCP-related serious adverse events (Dumonceau et al., 2020)
- Sedation/anesthesia related serious adverse events
- Other serious adverse events (procedure or product related)
- Adverse events during enteroscopy and ERCP procedure
- Adverse events of interest are: bleeding, mucosal damage and pancreatitis (including hyperamylasemia)

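### The SAP contains no severity cut, so it does not report the moderate-or-severe safety endpoint that the protocol defines for Phase B, and it assigns no confidence interval to any safety rate

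*SAP*

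**What the plan says.** **Protocol.** Section 3.1.3 defines Phase B safety as the incidence and number of subjects with "Serious Adverse Events (SAEs) and Device Deficiencies (DD) which meet the severity grading of moderate or severe for the following categories". The categories are enteroscopy-associated, ERCP-related, sedation or anaesthesia related, and other. The Trial Summary repeats the definition ("Device Deficiencies (DD) which meet the severity grading of moderate or severe for the following categories"). Section 4.1.3 also wants AE tables by system organ class, by relation, and "stratified by severity (mild, moderate, severe".

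Section 11.2.1 introduces its list of recorded items with "For each adverse event the following information shall be documented". The items are description, outcome, seriousness, duration, causality and any therapy. Severity is not among them.

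Section 1.2 announces a comparison of the safety data with published data, and section 3.2.3 names the Phase B reference procedures. Section 1.3 commits the team to checking for deviation from guideline frequencies: 0.08 to 9.7% for the major ERCP events and up to 24.6% for sedation-related events.

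**SAP.** Section 2.5 lists the four SAE groups without a grade, the last being "Other serious adverse events (procedure or product related". Section 3.4.3 codes seriousness and, for causality, states: "A frequency table will be presented showing the information on attribution of the AE to the PowerSpiral device". Section 3.7.1 says: "The frequencies of adverse events, serious adverse events and device deficiencies will be reported in summary tables". It then limits the breakdown: "Tabulations will be provided for system organ class and stratified by relation to the investigational product".

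For intervals, section 3.6 names Clopper-Pearson for four success rates. Section 3.5 has a general provision for intervals where they are appropriate. The legend of section 3.9 adds them to frequency tables only for a primary endpoint, which neither document identifies.

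**The concern.** The SAP sentence on breakdowns keeps two of the three dimensions in protocol 4.1.3 and leaves out severity. If the SAP is followed literally, the one safety endpoint the protocol defines does not appear in the report. It would have to be assembled after the data have been seen, or the pooled SAE rate would stand in for it.

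The planned literature comparison raises a second problem. Protocol section 1 cites complication rates of 4 to 12% and AE rates of 4% and 12.4% without event definitions. A bare percentage from about 100 patients does not show which of these it is compatible with. The reader also cannot tell in advance whether the study's all-grade AE rate, its SAE rate or its moderate-or-severe SAE rate will be placed beside them.

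**Working it through.** The plan states no safety precision or target to reproduce. Protocol 3.3.6 says the 100 subjects were not chosen on power. The check is therefore a comparison of the texts, followed by illustrative arithmetic.

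**Step 1: search the SAP for a severity cut.**

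| Place in SAP | What it holds | Severity? |
|---|---|---|
| 2.5 | Four SAE groups, procedural AEs, events of interest | No |
| 3.4.3 | Seriousness, attribution to device | No |
| 3.7.1 | System organ class, relation, special interest | No |
| 3.9, tables 11.3.1.2.1 and 11.3.1.2.2 | AEs and SAEs by category | No |
| 3.9, tables 11.3.1.4.1, 11.3.1.4.2, 11.3.1.7.1 and 11.3.1.7.2 | Relatedness | No |
| 3.9, 11.3.1.5.1 and 11.3.1.5.2 | Seriousness and its components | No |
| 3.9, listing 11.7.2 | All AE parameters | Only if the form has it |

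Seriousness is not severity, so the 11.3.1.5 outputs do not fill the gap. Moderate and severe SAEs are counted in the category and relatedness tables, but they cannot be separated there from mild ones.

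**Step 2: device deficiencies.** SAP 3.7.1 promises frequencies in summary tables. The only dedicated output in 3.9 is 11.3.1.7.3, a listing of free text. The two sections disagree.

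**Step 3: what the missing cut could do.** The documents give no share of mild SAEs, so the following rests on assumed shares. Take 12 of 100 subjects with an SAE, and let m be the fraction whose SAEs are all mild. The endpoint count is 12 × (1 − m).

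- m = 0: 12 subjects, 12% (exact 95% limits 6.4 to 20.0%)
- m = 0.25: 9 subjects, 9% (4.2 to 16.4%)
- m = 0.5: 6 subjects, 6% (2.2 to 12.6%)

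**Step 4: precision of a safety rate.** This uses the SAP's own efficacy method. For x events in n subjects, the lower limit is the 2.5% quantile of Beta(x, n − x + 1) and the upper limit is the 97.5% quantile of Beta(x + 1, n − x). For x = 0 the lower limit is 0 and the upper limit is 1 − 0.025^(1/n); at n = 100 this is 3.6%.

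| Events | n = 100 | n = 90 (assumed smaller set) |
|---|---|---|
| 0 | 0 to 3.6% | 0 to 4.0% |
| 4 | 1.1 to 9.9% | 1.2 to 11.0% |
| 8 | 3.5 to 15.2% | 3.9 to 16.8% |
| 12 | 6.4 to 20.0% | 7.1 to 22.1% |

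At n = 100 the intervals for 4 and 12 events overlap between 6.4 and 9.9%. The interval for 8 events contains both AE rates cited in protocol section 1 (4% and 12.4%).

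**The case against.** Several points can be made for the plan.

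- **SAEs are not left out.** They are tabulated by category and by relation to enteroscopy, ERCP, sedation and device. SAP 2.5 mirrors the variable list in protocol 4.1.3, which itself carries no threshold. This is true, but the same section 4.1.3 goes on to require the severity split, and section 3.1.3 sets the threshold.
- **Few SAEs may be mild.** Under the criteria in protocol 11.1.3 (death, life-threatening illness, permanent impairment, hospitalisation, intervention), the pooled table may lie close to the endpoint. That is possible. The documents do not settle it, so the size of the difference remains open.
- **Intervals can be computed by any reader.** Counts and incidences will be reported, and the study is exploratory with no margin. This stands as a reason for restraint: the missing interval is a reporting gap, not an invalid analysis. It still matters when the protocol plans to set these rates beside published ones.

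A reader might also infer three stronger things that the documents do not support:

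- **That severity is not collected.** Protocol 11.2.1 omits it, but the AE form is not available and listing 11.7.2 shows all parameters.
- **That device deficiencies will not be counted.** SAP 3.7.1 says they will; the fault is that 3.9 does not follow.
- **That Phase B has no reference to compare with.** Protocol 1.3 gives ERCP-specific frequencies and 3.2.3 names the reference procedures. What is missing is the pairing of a study rate with each reference and matched event definitions.

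**Conclusion.** The point holds. Followed as written, the SAP does not report the protocol's Phase B safety endpoint, because no severity cut exists anywhere in it. This conclusion rests on the texts alone.

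The numerical effect cannot be computed from the documents. Under assumed mild shares of 0 to one half, a pooled 12% would correspond to an endpoint of 12% down to 6%. The device-deficiency issue is an inconsistency between SAP 3.7.1 and 3.9. The interval issue is one of specification: neither SAP rule outside section 3.6 assigns an interval to a safety rate. The limits shown assume 90 or 100 analysed subjects and are reference points only. They are not evidence that the sample is too small for an exploratory registry.

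**What to change.** 1. Confirm that the AE form records severity for AEs and for device deficiencies, and state the scale. Align protocol 11.2.1 only if needed.
2. Add to SAP 3.7.1 and 3.9, on the safety population: subjects with at least one moderate or severe SAE, overall and in each of the four protocol categories; the mild/moderate/severe stratification of AEs from protocol 4.1.3; and a device-deficiency frequency table with the same cut, so that 3.9 matches 3.7.1.
3. Give 95% Clopper-Pearson intervals for these rates and for the overall subject-level AE and SAE rates.
4. Before database lock, state which of these rates will be placed, descriptively, beside each reference already cited in protocol sections 1 and 1.3. Note where event definitions cannot be matched.

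The cost is a few table shells and an interval column. A change to protocol 11.2.1 would need a written amendment with ethics committee approval under protocol section 6. Only if the form lacks severity would a new field and retrospective grading be needed.

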- **Handling** (Handling means the whole handling of the instrument (PowerSpiral scope + overtube + motor control unit) during preparation of the equipment and throughout the examination).
- **Instrument insertion** (Instrument insertion means how the instrument could be inserted).
- **Precision of positioning during therapy** (This means how precise and how stable the instrument could be positioned during a therapeutic intervention).

Clinical Investigation Plan

CIP Reference No.:2018-GI (OEKG) -01. The SAMISEN study - Final Version 03 - Date 28-Jun-2021

- **Time needed for procedure** (It means the time duration describes the start as entering the endoscope in the mouth until withdrawal which suppose as stop point).
- Staff and resources required for procedure.

At visit 4

Visit 4 is the hospital discharge visit. The patient is ready to leave the hospital and the status shall be documented.

The following data will be documented:

- Date of the hospital discharge examination.
- Actual discharge date.
- if the patient has recovered from the examination.
- Describe new (Serious) Adverse Event if any
- Clinical signs or symptoms of pancreatitis e.g. elevated Lipase/Amylase (if measured post-procedure as medical standard in your hospital).
- Specify if the patient get further treatment from the referral physician or if additional specialist(s) will be involved.

The investigator will ensure that the patient receives further medication as necessary and can be discharged from hospital and consigned to GP's or medical specialist's care.

Finally, the investigator shall to sign off the eCRF to confirm that the data is complete and accurate.

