3.4.6 Deviations from medical standard

The observational character of this registry study does not require any additional clinical procedure or tests beyond standard of care. Any deviation for medical reasons shall be documented in the eCRF.

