11.4 Anticipated Adverse Events

Foreseeable risks include those typically associated with ERCP performed under general anesthesia or sedation.

The following device and process related events were observed in previous Investigator-Initiated-Trials with PowerSpiral and reported in the context of post-market surveillance. The SAMISEN study will contribute and extend the safety profile of the PowerSpiral device.

Clinical Investigation Plan

CIP Reference No.:2018-GI (OEKG) -01. The SAMISEN study - Final Version 03 - Date 28-Jun-2021

Table 2 List of anticipated (Serious) Adverse Events

- tissue damage
- mucosal damage
- laceration
- inflammation
- bleeding
- hematoma
- perforation
- penetration
- infection
- pain (such as abdominal pain sore throat and odynophagia)
- abdominal distention
- discomfort (such as abdominal discomfort and swallowing discomfort)
- indigestion
- nausea
- vomiting
- cardiovascular problem (bradycardia, tachycardia, hypotension and hypertension)
- dysphagia
- respiratory system disorder (such as aspiration pneumonia, cough, hypoxemia, respiratory instability and mediastinal emphysema)
- pancreatitis
- fever
- hyperamylasemia
- hyperlipasemia
- intestinal obstruction
- intestinal necrosis
- intussusception
- parotitis
- hiccup
- electrical shock
- burn (operator)
- physical deconditioning
- distress
- allergy
- heat injury
- exposure
- acute pancreatitis
- cholangitis
- aspiration pneumonia
- CO2 narcosis
- atrioventricular block
- surgery (as a result of perforation, laceration, bleeding, tissue damage, etc)
- bruise (Health Care Professional)
- bleeding (Health Care Professional)

Clinical Investigation Plan

CIP Reference No.:2018-GI (OEKG) -01. The **SAMISEN** study - Final Version 03 - Date 28-Jun-2021

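### The special-interest count of pancreatitis includes hyperamylasemia, which is seen only where enzymes are measured locally, so that line cannot be read as a pancreatitis rate

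*SAP*

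**What the plan says.** Protocol 4.1.3 names the adverse events of interest as "bleeding, mucosal damage and pancreatitis (including hyperamylasemia"), and SAP 2.5 repeats the definition. SAP 3.7.1 makes it a single patient count, "Number of patients with pancreatitis (including hyperamylasemia"). SAP 3.9 plans it as Table 11.3.1.8.1 (all adverse events) and Table 11.3.1.8.2 (serious only). Both give absolute and relative frequencies on the safety population, which SAP 3.1 defines as everyone with at least one enteroscopy.

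On measurement, the Visit 4 list in protocol 3.4.2 asks for "Clinical signs or symptoms of pancreatitis e.g. elevated Lipase/Amylase (if measured post-procedure as medical standard in your hospital"). Protocol 3.4.6 adds that the registry "does not require any additional clinical procedure or tests beyond standard of care". The SAP's laboratory sections (3.4.4 and 3.7.2) are marked as not applicable, and SAP 3.4.1 replaces no missing data. Neither document gives an enzyme threshold, a sampling time, diagnostic criteria for pancreatitis or a denominator of tested patients.

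The anticipated-event list in protocol 11.4 shows "hyperamylasemia", hyperlipasemia and pancreatitis as separate entries.

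**The concern.** The line joins a clinical complication to a laboratory finding, and the laboratory finding exists only where someone looks for it. The absence of an adverse event entry is a non-event, not a missing value, so the missing-data rules do not help. An untested patient is simply counted as free of hyperamylasemia.

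Two hospitals with the same patients and the same pancreatitis frequency could then report different rates. With the 4 to 5 sites foreseen in protocol 1.2, one site's routine governs roughly a fifth to a quarter of the patients if enrolment is even.

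This matters because protocol 1.2 intends to compare safety data with guidelines or literature. Protocol 1.3 commits the study team to noticing early whether safety departs from published frequencies. That section lists pancreatitis, without hyperamylasemia, among major ERCP adverse events with incidences of 0.08 to 9.7%.

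**Working it through.** The documents state no rate for this event, and the 100 patients were not chosen on power (protocol 3.3.6). There is no figure to reproduce, so the check is an illustration under stated assumptions.

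**Inputs, none of them given in the documents**
- p = true pancreatitis rate, assumed 4%.
- h = share of tested patients without pancreatitis whose isolated enzyme rise is counted as an event, varied from 0 to 20%.
- m = share of patients with a post-procedure measurement, varied from 25 to 100%.

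The model assumes that pancreatitis is always detected and that testing does not depend on outcome.

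**Pooled rate** = p + (1 − p) × h × m

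| h | m = 25% | m = 50% | m = 100% |
|---|---|---|---|
| 0% | 4.0% | 4.0% | 4.0% |
| 5% | 5.2% | 6.4% | 8.8% |
| 10% | 6.4% | 8.8% | 13.6% |
| 20% | 8.8% | 13.6% | 23.2% |

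Examples: 0.04 + 0.96 × 0.05 × 1 = 0.088, and 0.04 + 0.96 × 0.20 × 1 = 0.232.

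**One site's habit.** If one of four equal sites starts or stops routine measurement, m moves by 0.25. The pooled rate then moves by 0.96 × h × 0.25, which is 1.2 points at h = 5%, 2.4 at 10% and 4.8 at 20%.

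**Against the protocol's range.** The pooled rate passes 9.7% once h × m exceeds (0.097 − 0.04) / 0.96 = 5.9%, with pancreatitis unchanged. The 0.08 to 9.7% range covers five kinds of event, so this only shows how far the line can drift. It is not a test against a pancreatitis benchmark.

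**After splitting.** The pancreatitis row is p = 4% whatever h and m are, provided the diagnosis does not itself depend on enzymes. The enzyme row over measured patients is (1 − p) × h. For h = 20% this is 0.96 × 0.20 = 19.2%, again independent of m.

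**The case against.** The strongest reply is that pancreatitis is largely recoverable elsewhere. Protocol 11.2.1 offers pancreatitis as a selectable term and does not list hyperamylasemia. Tables 11.3.1.2.1 and 11.3.1.2.2 report events by category, Table 11.3.1.3 lists other events as free text, and Listing 11.7.2 shows every event. Table 11.3.1.8.2 also gives a serious-only version. Nothing says that the pooled line is the figure to be set against the literature; the Phase B safety parameter in protocol 3.1.3 concerns serious events and device deficiencies graded moderate or severe. This stands, and it confines the defect to one line. The recovery is only partial. The Visit 4 item treats a raised enzyme as a sign of pancreatitis, so an isolated rise might be entered under that term. The serious-only table drops non-serious pancreatitis and keeps the pooled definition.

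A second reply is that few isolated rises may be counted at all. The note in protocol 11.1.1 treats a laboratory change as clinically significant only if it suggests new or worse disease or needs active management. That could push h towards zero. However, close observation is among its examples of active management, and protocol 11.2.1 asks investigators to note any abnormal laboratory finding. How strong this filter is remains open, which is why the table starts at h = 0.

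Third, variable testing is inherent in an exploratory registry that adds no procedures. That is true, but the remedy concerns reporting, not testing.

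A reader might infer that the line measures testing habits and not pancreatitis. The documents do not support that: the count contains both, and the balance depends on p, h and m, none of which they give.

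**Conclusion.** The point holds for the special-interest line and its two tables. As written, the pooled rate depends partly on which sites measure enzymes, and it cannot be read as, or compared with, a published pancreatitis rate. It does not follow that the study's pancreatitis data as a whole are unusable, or that its safety comparison fails.

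The size is unknown. The illustration runs from no effect (4% pooled against an assumed 4% pancreatitis rate) to 23.2%, and the upper end requires that 20% of the other patients have a counted isolated rise and that everyone is tested. The distortion shrinks towards zero if investigators apply the clinical-significance note strictly. The change is worth making because it is cheap and the line otherwise has no clear meaning.

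**What to change.** In SAP 3.7.1 and Tables 11.3.1.8.1 and 11.3.1.8.2, replace the pooled line with two rows.

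1. **Pancreatitis**, over the whole safety population, under a stated definition that does not rest on an enzyme rise alone. Without that definition the row could still follow local testing.
2. **Hyperamylasemia or hyperlipasemia without pancreatitis**, with patients who had a post-procedure measurement as denominator and the number measured shown per site. Naming both enzymes also settles whether an isolated lipase rise counts, which the present wording leaves open.

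Align SAP 2.5 and protocol 4.1.3 with the split. Add a yes/no item for post-procedure enzyme measurement to the discharge form if the CRF does not already hold it; the CRF is not among the documents reviewed.

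The cost is minor SAP and form wording, one extra row, and a smaller, less precise denominator for the enzyme row. No new tests are needed.
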